4.16.1.4 Multi-center Studies

This study will be conducted at approximately 35 sites in the United States (US) and Europe. To avoid confusion between the terms investigative sites and body sites, this document, as well as all summaries and analyses in statistical outputs, will use the word ‘center’ for study investigative sites. Since the primary endpoint will be determined on histopathology and centralized reading, the centers will not be part of the primary endpoint analysis.

A number of endpoints will have additional analyses by center; this will be indicated on a case by case base within each analysis. For these analyses, centers with small numbers of patients may be combined, for instance to country level. This combining will be identical for all applicable analyses.

4.16.1.5 Adjustments for Covariates

There will be no adjustment for covariates in the primary analysis.

4.16.1.6 Interim Analyses

Once 60% of the planned 190 positive cases have PSA levels recorded in the eCRF, the proportion of included patients with a PSA <1 ng/mL will be assessed. If this proportion exceeds 60% then investigators will be told to stop further enrolment of this cohort. There will be no formal TFL delivery for this interim.

4.16.2 Primary Efficacy Variable

The primary analysis will be performed using the EAP.

The joint hypothesis is as follows:

Parexel International

Blue Earth Diagnostics Ltd

BED-PSMA-302

Statistical Analysis Plan

H_0 : CDR $\leq 36.5\%$ or PPV $\leq 62.5\%$ versus H_1 : CDR $> 36.5\%$ and PPV $> 62.5\%$

Both CDR and PPV will be displayed using a point estimate (expressed in percentage), two sided 95% CIs and a one-sided 2.5% hypothesis test for each reader.

For CDR, the two-sided 95% CIs will be exact intervals. A one-sided exact binomial test p-value will be provided for each reader for each CDR.

For PPV, the 95% CIs and p-values will be estimated using clustered binary data methodology (Section 4.16.1.3). Both CIs and binomial test p-value will be displayed for each reader.

For the study to be considered a success, the p-values for both endpoints must be statistically significant (one-sided 0.025) for at least two out of the three readers (same readers for both CDR and region level PPV). The analysis will be based on the p-value cut-offs applied to both endpoints at the interim and final analysis, if needed (Section 4.16.1.6).

In addition to the individual blinded readers, their majority CDR and PPV will be analyzed (see Section 4.14 for majority assessment).

4.16.3 Secondary Efficacy Variables

4.16.3.1 Patient level CDR and region level PPV of rhPSMA-7.3 (^{18}F) PET in the subgroup of patients who have negative baseline conventional imaging.

This will be a repeat of the primary efficacy using patients from the EAP with negative baseline conventional imaging (according to site reads). The point estimates and two-sided 95% CIs of CDR and PPV will be displayed for each of the blinded independent readers and their majority.

4.16.3.2 Patient level CDR and region level PPV of rhPSMA-7.3 (^{18}F) PET for recurrence in those patients with and without reference standard histopathology available.

For CDR, this will be repeats of the primary efficacy using patients from the EAP and one more condition:

1. Patients with standard histopathology for SoT assessment
2. Patients with no standard histopathology for SoT assessment

For PPV, this will be repeats of the primary efficacy using patients from the EAP and one more condition:

1. Regions with standard histopathology assessment
2. Regions with no standard histopathology assessment

The point estimates and two-sided 95% CIs of CDR and PPV will be displayed for each set of patients for each of the blinded independent readers and their majority.

4.16.3.3 Patient level CDR and region level PPV of rhPSMA-7.3 (^{18}F) PET stratified by PSA level.

This will be repeats of the primary efficacy using patients from the EAP. The last PSA level before the PET scan will be used to stratify the patients (see Section 4.10 for categories). The point estimates

Parexel International

Blue Earth Diagnostics Ltd

BED-PSMA-302

Statistical Analysis Plan

and two-sided 95% CI of CDR and PPV will be displayed for each set of patients for each of the blinded independent readers and their majority.

4.16.3.4 CDR of rhPSMA-7.3 (¹⁸F) PET in the following regions: local recurrence, pelvic lymph nodes, other.

This analysis will use the EAP. The analysis will be performed for each region and for each of the blinded independent readers and their majority. The frequency of confirmed detection will be summarized, including proportion and exact CI of the proportion.

4.16.3.5 Percentage of patients in whom rhPSMA-7.3 (¹⁸F) PET imaging results changed the intended patient management (major and other changes).

This analysis considers patients in the EAP who have documented patient management plans in the EDC for before and after the rhPSMA-7.3 (¹⁸F) PET scan. Major and other changes in management plan (see section 4.7) will be summarized showing frequency, proportion (including 95% CI) overall.

4.16.3.6 Reader kappa statistics of rhPSMA7-3 (¹⁸F) scan interpretation by the blinded independent readers.

This analysis considers all patients within the EPSP.

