8.2 Blinding

The local sites will not be blinded and the patients will not be randomized to study treatment. All rhPSMA-7.3 (¹⁸F) PET images from all study sites will be submitted for a randomized, blinded image evaluation.

The rhPSMA-7.3 (¹⁸F) images will be randomized and read by three blinded, independent central PET readers who have received specific training on rhPSMA-7.3 (¹⁸F) and are also blinded to results of conventional imaging.

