Historical conventional imaging, acquired more than 90 days before Visit 1, if available and if performed as part of the patient's PCa staging and treatment in the prior ~24 months, can be used to establish SoT where a biopsy cannot be obtained.

Patients will be asked to provide these pre-existing images, if these were done at another institution. If done at the study site, these images will be made available by the study site.

9.1.6 *Confirmatory Imaging*

In cases where historical conventional imaging is not available or inconclusive for comparison to baseline imaging, rhPSMA-7.3 (¹⁸F) directed (for confirmation of lesion location only) follow-up confirmatory imaging of the site(s), will be acquired at the discretion of the local investigator(s), with reference to the Study Imaging Manual. Examples of confirmatory imaging modalities include specific body region MRI (including functional or multi-parametric MRI), CT, Axumin, NaF, etc (see [Sections 9.2.2.2](#) and [9.2.2.3](#)).

9.1.7 *rhPSMA-7.3 (¹⁸F) PET Scan*

After enrollment (either before or after conventional imaging; see [Section 9.1.5](#)), all patients will receive an IV bolus of rhPSMA-7.3 (¹⁸F) injection and undergo a PET scan as described in the Study Imaging Manual.

9.1.8 *Image Interpretation*

For biopsy/SoT confirmation guidance:

- Due to logistical and medical liability considerations, results of the image interpretation by local site readers must be used when patients are triaged for invasive biopsy procedures. rhPSMA-7.3 (¹⁸F) PET imaging will be interpreted by on-site readers who have received specific training on rhPSMA-7.3 (¹⁸F).

For determination of the primary endpoint:

- rhPSMA-7.3 (¹⁸F) PET images will be blinded, randomized, and read by three trained independent central PET readers who have received specific training on rhPSMA-7.3 (¹⁸F) scans and are blinded to results of conventional/confirmatory imaging.

9.1.9 *Biopsy/Surgery*

If rhPSMA-7.3 (¹⁸F) PET shows one or more sites of recurrence, the most accessible and feasible* (as judged by the local investigator) lesion(s) will be biopsied under radiological guidance. In patients with multiple rhPSMA-7.3 PET-positive regions, attempt should be made, where safe and medically feasible, to obtain histopathology on the most accessible and feasible lesion(s) in each region (prostate bed, pelvic lymph nodes, and other [bone, extra-pelvic lymph nodes, viscera and other soft tissues]).

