10.2 Visit 2 (Day 1; IP Administration)

1. Record any changes in concomitant medication since screening (omit if Visit 1 and Visit 2 are combined; see [Section 10.3](#)).
2. Perform and record pre-IP administration vital signs.
3. Record patient's body weight pre-IP administration.
4. Ask about and record any AEs since screening (omit if Visit 1 and Visit 2 are combined; see [Section 10.3](#)).
5. IP administration (IV bolus rhPSMA-7.3 [¹⁸F] injection).
6. PET scan as described in the Study Imaging Manual.
7. Record any AEs occurring during the scan process.
8. Perform and record post-IP administration vital signs.
9. Schedule patient for Visit 3 within 7 days post-IP administration.

Optional Visit 2(a): If not already performed, obtain baseline conventional imaging up to 2 weeks following IP administration. Any conventional imaging performed up to 90 days prior to Visit 1 and up to and including Visit 2(a) will be considered baseline conventional imaging.

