2.2 Secondary Objective(s)

The secondary objectives of the study are to:

1. Assess the patient level CDR and region level PPV of rhPSMA-7.3 (¹⁸F) PET in the subgroup of patients who have negative baseline conventional imaging (classified at the site level).
2. Assess the patient level CDR and region level PPV of rhPSMA-7.3 (¹⁸F) PET separated into subgroups of patients with reference standard histopathology available and unavailable.
3. Assess the patient level CDR and region level PPV of rhPSMA-7.3 (¹⁸F) PET stratified by PSA level.
4. Assess the CDR of rhPSMA-7.3 (¹⁸F) PET on a region level.
5. Assess the impact of rhPSMA-7.3 (¹⁸F) results on the intended clinical management of study participants using a clinician survey.
6. Assess the inter- and intra-reader agreement of rhPSMA-7.3 (¹⁸F) scan interpretation by the blinded independent readers.
7. Assess the safety of rhPSMA-7.3 (¹⁸F) injection in patients.

Parexel International

Blue Earth Diagnostics Ltd
BED-PSMA-302

Statistical Analysis Plan

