4.2 General Presentation Considerations

‘Baseline’ is defined as the last available pre-IP administration assessment, with the exception of baseline imaging which may be performed up to 2 weeks following IP administration if conventional imaging has not been performed within 90 days prior to enrolment.

‘End of Study’ is defined as the last available post-treatment assessment.

‘Study Day’ will be calculated relative to the date of rhPSMA-7.3 (¹⁸F) injection day, and is equal to:

- Assessment Date – IP Administration Date + 1 if the assessment date is on or after IP administration date.
- Assessment Date – IP Administration Date, if the assessment date is before IP administration date.

(i.e. rhPSMA-7.3 IP Administration Date = Study Day 1, the day before IP administration date = Study Day –1))

Continuous data will be summarized in terms of the mean, standard deviation (SD), median, minimum, maximum and number of observations, unless otherwise stated. Continuous data (e.g. counts) that are expected to be skewed will be presented in terms of the maximum, upper quartile, median, lower quartile, minimum and number of observations. The minimum and maximum will be reported to the same number of decimal places as the raw data recorded in the database. The mean, median, lower quartile and upper quartile will be reported to one more decimal place than the raw data recorded in the database. The SD will be reported to two more decimal places than the raw data recorded in the database. In general, the maximum number of decimal places reported shall be four for any summary statistic, irrespective of the previous rules.

Categorical data will be summarized in terms of the number of subjects providing data at the relevant time point (n), frequency counts and percentages. Any planned collapsing of categories will be detailed in the SAP text and the data displays.

Percentages will be presented to one decimal place. Percentages will not be presented for zero counts. Percentages will be calculated using n as the denominator. If sample sizes are small, the data displays will show the percentages, but any textual report will describe frequencies only.

Confidence intervals (CI) will be presented to one more decimal place than the raw data, CI for percentages will be to one decimal place.

Changes from baseline in categorical data will be summarized using shift tables where appropriate.

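### For some patients the PET result may influence who counts as negative on baseline conventional imaging, because unblinded sites classify scans acquired up to two weeks after PET

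*SAP*

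**What the plan says.** **Who classifies.** SAP 4.16.3.1 selects patients "using patients from the EAP with negative baseline conventional imaging (according to site reads"). The objective in SAP 2.2 says the same: "negative baseline conventional imaging (classified at the site level").

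**What counts as baseline.** Protocol 10.2 lets the site "obtain baseline conventional imaging up to 2 weeks following IP administration" if this was not done before, and adds that any conventional imaging from 90 days before Visit 1 "up to and including Visit 2(a) will be considered baseline conventional imaging". SAP 4.12.1 repeats that rule, and Protocol 10.3 sets the same two-week limit for the combined visit. SAP 4.2 makes imaging the one exception to its pre-dose definition of baseline, "baseline imaging which may be performed up to 2 weeks following IP administration", but only where no conventional imaging was done in the 90 days before enrolment.

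**What the site knows.** Protocol 8.2 states: "The local sites will not be blinded and the patients will not be randomized to study treatment". Under Protocol 9.1.8, "results of the image interpretation by local site readers must be used when patients are triaged for invasive biopsy procedures", so the PET is read and acted on locally. PET results are discussed with the patient at Visit 3, within 7 days (Protocol 10.4). Site review of historical and baseline imaging is listed among the procedures within 45 days after injection (Protocol 10.5).

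**Which reads are blinded.** The central PET readers are blinded to conventional imaging (Protocol 8.2 and 9.1.8). The central read of conventional imaging serves the standard of truth and is directed by the PET findings (SAP 3.2.2.3).

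**Status.** Secondary and exploratory endpoints are summarized descriptively; kappa statistics are used for reader agreement (Protocol 16.5).

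**The concern.** A subgroup meant to show how a test performs where conventional imaging found nothing should be fixed before the result of that test is known. Here a conventional scan can be acquired after PET, classified by a site that has already read the PET, and still set baseline status. A site that knows where PET was positive may call a subtle finding there, and the patient then leaves the negative subgroup. It may also discount an equivocal finding where PET was silent, and the patient then stays in.

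The trial aims to establish performance whatever conventional imaging shows (Protocol 2), and this subgroup is the first secondary endpoint. The same idea of a negative baseline underlies the exploratory detection-rate subgroup (SAP 4.16.4.1) and the upstaging count (SAP 4.16.4.3).

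Elsewhere the SAP holds to pre-PET values. PSA strata use the last PSA before the scan (4.16.3.3), and a pre-scan management plan dated after Day 1 is not accepted as valid (4.7, Table 2).

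**Working it through.** **Step 1: the text.** Set side by side, the sections give the following.

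- *Acquisition.* The two-week limit governs when the scan is acquired. Neither document sets a date for the site read. A scan acquired before PET could therefore also be read, or reviewed again, with the PET known.
- *Who can be affected.* Under SAP 4.2 a post-PET scan is baseline only if there was none in the preceding 90 days. Under Protocol 10.2 and SAP 4.12.1, any conventional scan up to Visit 2(a) is baseline. On the wider rule, a further scan could change the status of a patient whose earlier imaging was negative.
- *Combining scans.* In the SAP 4.12.1 summary, one positive result outweighs negative results within a modality. SAP 4.16.4.1 takes negative to mean no lesion at all. SAP 4.16.3.1 states no combination rule of its own.
- *Fallback.* No PET-blinded read of conventional imaging is described that could replace the site read.

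**Step 2: size.** The documents give no expected size, CDR or PPV for this subgroup, so there is no figure of theirs to reproduce. What follows is an illustration.

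Inputs:
- c, the CDR under a classification free of PET: 49% (overall planning value) or 29% (planning value for PSA <1 ng/mL), both from Protocol 4.2 and SAP 4.18.1.
- P, the PPV: 73.5% from the same sections. It is a region-level figure, used here as a patient-level stand-in.
- f, the share of the subgroup imaged after PET: assumed 10-50%.
- q, the share of true-positive patients among those who are re-labelled positive because PET is known: assumed 10-50%.

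If only true-positive patients leave the subgroup:

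- CDR = c(1 - fq) / (1 - c·fq)
- PPV = P(1 - fq) / (1 - P·fq)
- the upstaging count falls by the fraction fq

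| f | q | fq | CDR from 49% | CDR from 29% | PPV from 73.5% | Fall in upstaging count |
|---|---|---|---|---|---|---|
| 10% | 10% | 0.010 | 48.7% | 28.8% | 73.3% | 1% |
| 25% | 30% | 0.075 | 47.1% | 27.4% | 72.0% | 7.5% |
| 50% | 50% | 0.250 | 41.9% | 23.5% | 67.5% | 25% |

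Worked last row: 0.49 × 0.75 / (1 - 0.49 × 0.25) = 0.3675 / 0.8775 = 41.9%.

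**Step 3: other reader behaviour.**

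- *False-positive patients leave at the same rate.* PPV stays at 73.5%. With d = 0.49 / 0.735 = 0.667, CDR = c(1 - fq) / (1 - d·fq), which gives 48.8% at fq = 0.01 and 44.1% at fq = 0.25.
- *True-positive patients are kept in.* An equivocal conventional finding away from the PET lesion is discounted because PET was silent there. If those retained number fq times the true positives already in the subgroup, CDR = c(1 + fq) / (1 + c·fq): 0.4949 / 1.0049 = 49.2% at fq = 0.01, and 0.6125 / 1.1225 = 54.6% at fq = 0.25.

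The sign therefore depends on how sites read, which the documents do not settle.

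**The case against.** Several objections carry weight.

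- **Post-PET imaging is mainly a fallback.** Visit 2(a) is optional and is meant for patients without imaging in the prior 90 days; imaging may also take place between Visit 1 and PET. This stands. Patients imaged and read before PET are unaffected unless a further scan is added within the window.
- **The mechanism is inferred.** No section says that the reader of the conventional scan has the PET result, and the Visit 3 discussion is a clinical review, not an image read. Site reading instructions may sit in the Study Imaging Manual, which is not available here. This also stands, but neither document cites such a safeguard for this classification.
- **Acquisition date is not read date.** Restricting to scans acquired before PET does not remove a pre-PET scan read late. This is correct, so the restriction closes one route and not all.
- **The link to upstaging is not explicit.** SAP 4.16.4.3 refers only to a negative baseline scan, while the site read is named in 4.16.3.1 and 4.16.4.1. That the same classification applies is likely but not stated.
- **A pre-PET subgroup is selected too.** It favours patients already imaged, in a trial that places PET in the initial workup. This is a reason to show both definitions rather than replace one.

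A reader might infer that PET decides who is in the subgroup, or that the bias flatters the product. The documents support neither: they leave open an influence on some patients, and the scenario in which true positives leave would lower the reported CDR.

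**Conclusion.** The point holds in limited form. For some patients, membership of the baseline-negative subgroup may be influenced by the PET result, since unblinded sites classify scans that may be acquired after PET and no rule separates the two reads. This applies to SAP 4.16.3.1 and 4.16.4.1 and, apparently, to 4.16.4.3.

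The size is unknown. Under the assumed ranges in which true-positive patients leave, CDR shifts by 0.3 to 7.1 points from 49% (49 - 48.7 and 49 - 41.9), and PPV by 0.2 to 6.0 points from 73.5%. These ranges rest entirely on assumed values of f and q, and the direction is not fixed.

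It would be wrong to carry the point over to the co-primary tests. They do not use this subgroup, and PET positivity there comes from blinded central readers. The analyses affected are descriptive. This is a low-priority improvement that is cheap to make.

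**What to change.** In SAP 4.16.3.1, 4.16.4.1 and 4.16.4.3:

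1. Report the number of patients whose baseline status rests on a conventional scan acquired after the PET date. Separate those with only a post-PET scan from those whose status was changed by one.
2. Present CDR, PPV, detection rate and upstaging counts, as each section requires, with status classified only from scans acquired on or before the PET date and, where a read date is available, read before PET. Show this beside the current definition, with post-PET-only patients in a separate row.
3. State the rule for combining several scans and modalities into one patient status, and say in 4.16.4.3 whether the site read applies.
4. Add the acquisition date to the baseline imaging listing in 4.12.1. The historical and confirmatory imaging listings (4.12.2 and 4.12.3) already show dates; the baseline listing does not mention them. Dates should exist, because the 90-day and two-week windows cannot be applied without them. Read dates are mentioned in neither document and may not have been collected.

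The cost is SAP wording and a little extra table output, with no change to trial conduct. The pre-PET subgroup will be somewhat smaller and weighted to patients already imaged before PET, and a pre-PET scan read late will remain in it unless read dates are available.

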4.16.3.6.1 Inter-reader agreement analysis

The Cohen's kappa statistic will be calculated to assess pairwise agreement between any 2 readers, including 95% exact CIs, giving 3 Kappa statistics (SAS® nomenclature: simple kappa). In addition, the Fleiss' kappa across the 3 readers, including 95% (approximate) CIs will be shown (SAS® nomenclature: overall kappa Coefficient).

This same calculation will be repeated for the regions:

Prostate/Prostate Bed

Pelvic Lymph Nodes

Other Sites

 Other: Lymph nodes outside pelvis

 Other: Soft Tissue/parenchyma

 Other: Bones

4.16.3.6.2 Intra-reader agreement analysis

Cohen's Kappa will be used to assess intra-reader agreements in the first read and the repeat read of 10% of the randomly selected images for each of the three readers.

Parexel International

Blue Earth Diagnostics Ltd
BED-PSMA-302

Statistical Analysis Plan

4.16.4 Exploratory Efficacy Variables

4.16.4.1 The overall patient level detection rate (without SoT confirmation), including detection rate subgroup analyses of patients: a) who have negative baseline conventional imaging (according to site read), b) with reference standard histopathology available and unavailable, and detection rate stratified by PSA level and assessed by region.

This concerns several similar analyses. In each analysis the frequency of patients with a PET positive lesion will be counted, proportion of positive patients including exact CI will be provided. Each analysis will be performed for each of the blinded independent readers and their majority.

- patients in the FSP who have PET scan and who have negative (no lesions detected at all) baseline conventional imaging.
- patients in the FSP who have PET scan and have reference standard histopathology.
- patients in the FSP who have PET scan and do not have reference standard histopathology.
- For each region (local recurrence, pelvic lymph nodes, other) patients in the FSP who have PET scan using subgroups by PSA levels (Section 4.10).

4.16.4.2 Patient level PPV in which a TP patient is defined as having at least one TP region, regardless of any coexisting FP regions.

This concerns all patients in the EAP. The patient level PPV frequency and proportion, including exact CIs will be provided for each of the blinded readers and their majority.

4.16.4.3 The number of positive rhPSMA-7.3 (¹⁸F) scans compared to conventional imaging in defined regions, leading to upstaging of the patient a) post-RP; b) post--RT.

This concerns patients with negative baseline scan in subgroups of the EAP with an extra subgroup condition, for a) the patient has had RP (with or without RT), for b) the patient has had RT (without RP) or c) patient has other therapies. (For definitions of RT and RP, see Section 4.8). The patients will be counted if they have any TP lesion in either of the regions (local recurrence, pelvic lymph nodes, other) for each of the blinded readers and their majority.

4.16.4.4 Patient and regional level detection rates of rhPSMA-7.3 (¹⁸F) PET.

This concerns the subgroup of patients in the FSP who have a PET scan. The regions analysis will concern local recurrence, pelvic lymph nodes and other. The frequency of detection, detection rate including exact CI will be determined for each of the blinded readers and their majority.

4.16.4.5 Patient and regional level detection rates of rhPSMA-7.3 (¹⁸F) PET as a function of PSA, prior Gleason score and PSAdt in a) post-RP; b) post-RT patients.

This concerns patients in subgroups of the EPSP with an extra subgroup condition, for a) the patient has had RP, for b) the patient has had RT (see Section 4.8). The regions analysis will concern local

Parexel International

Blue Earth Diagnostics Ltd
BED-PSMA-302

Statistical Analysis Plan

recurrence, pelvic lymph nodes and other. Patients will be analyzed by PSA category (Section 4.10), by total (biopsy and surgery) Gleason score (Section 4.9) and by PSAdt category (Section 4.10) for each of the blinded readers and their majority.

